## 5. STATISTICAL METHODS

## 5.1 Statistical Hypothesis and Determination of Sample Size

The primary efficacy analysis will be to compare PFS distributions of seribantumab in combination with physician's choice of fulvestrant and/or exemestane versus control (fulvestrant and/or exemestane alone). The study is designed to test superiority with the null hypothesis of no differences in progression-free survival distributions using investigator assessed disease progression between the treatment and control arm.

The primary PFS analysis will be performed using a stratified log-rank test, where stratification factors are prior chemotherapy use (yes, no), chemotherapy backbone (exemestane or fulvestrant), and geographic region (US, Non-US/Non-Asia, Asia). The stratified log rank test will be performed using a one-sided significance level at 0.025.

Interim analysis will be conducted when reporting approximately 50% (approximately 16 months from first patient) of the final PFS events have been observed in the primary efficacy population. Type II error will be preserved using a Lan-DeMets (non-binding) beta spending function approach with an O'Brien-Fleming boundary. Non-binding for the futility analysis implies that the futility boundary will be constructed in such a way that it can be overruled if desired by the DMC without inflating the type I error rate and without decreasing power. The interim will be a futility analysis only. The planned interim analysis is detailed in section 5.1.1.

Since the boundary is dependent on the number of PFS events the actual boundary used will be re-calculated based on the number of actual PFS events achieved at the time of the interim analysis. The DMC will be responsible for evaluating the interim analysis and making a recommendation about early termination due to observed study results as outlined in the DMC charter.

Approximately 195 PFS events are be required to have at least 95% power to detect a 43% risk reduction (mPFS: 4 v 7; HR  $\leq$  0.57) for patients receiving the combination of seribantumab plus exemestane or fulvestrant versus exemestane or fulvestrant alone, using a one-sided, stratified log-rank test at a significance level of 0.025, assuming a 2:1 ratio. An accrual of 24 months in length to obtain the required number of 195 PFS events is estimated to be achieved at approximately 30 months with a total sample size of 286 patients.

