# 5. Study Treatment

### 5.1. Method of Assigning Patients to Treatment Groups

If a patient is determined to be HRG positive, investigators will determine whether all other study enrollment criteria have been fulfilled. Upon completion of screening assessments, eligible, patients will be randomized 1:1 to the treatment or control arm using an Interactive Web Response System (IWRS). Randomization will be stratified based on bone-only disease (yes, no) and geographic status (US, non-US).

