# 10.2. Statistical Hypothesis and Determination of Sample Size

The primary hypothesis is to test for differences in progression-free survival (PFS) distributions.

A stratified log-rank test will be used to analyze PFS differences with the stratification factors in the model: Statistical significance will be determined by using a one-sided type I error of 0.10. A stratified Cox proportional hazards model will be used to estimate the hazard ratio using geographic region (US, non-US) and bone-only disease (yes, no) as stratification factors.

The median PFS for the control arm (fulvestrant + placebo) is assumed to be 4.0 months in this patient population. A total of 58 PFS events will be required across two treatment arms randomized in a 1:1 ratio giving 80% power to detect a hazard ratio (HR)  $\leq$  0.57 (mPFS: 4 v 7), assuming a 1-sided significance level of 0.10. Approximately 200 patients will need to be screened in order to accrue 80 randomized in approximately 16 months with a total study duration of 20 months.

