## 1.2 Study Design

This study is a double-blind, placebo-controlled, phase 3 trial of exemestane or fulvestrant with or without seribantumab in postmenopausal patients with hormone receptor-positive, heregulin positive (HRG+), HER2 negative metastatic breast cancer whose disease progressed after prior systemic therapy.

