## 5.3.1 Data Cut-off

A database snapshot will be determined at the time of the confirmed number of PFS events: 195 final. The snapshot will not be performed until the minimum number of PFS events have occurred. The snapshot will include all data entered and cleaned up to that particular point in the study and data will not be changed, edited, or updated on or prior to this particular date. A separate snapshot of this data will be maintained in the biostatistics and programming area. Patients that have completed the study will require investigator signature. Continuing patients will have data reviewed and approved. Data entered after the data cut-off dates will continue to be cleaned but not reported at the time of the interim or final analysis.

A final database lock will be performed upon determination of the final PFS event. Any necessary changes to previously entered data will be documented. The final database lock will include all data for all timepoints and will be conducted at a later timeframe. Site investigators will provide signatures for any remaining patient data which was outstanding at the time of soft lock.

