## 5.5 Efficacy Analysis

## 5.5.1 Primary Efficacy PFS Analysis

PFS analysis will be performed using a stratified log-rank test. Stratification factors will include: prior chemotherapy use (yes, no), chemotherapy backbone (exemestane or fulvestrant), and geographic region (US, Non-US/Non-Asia, Asia). Patients with missing stratification factor will be included in the primary efficacy analysis by merging them into the largest category for that factor. Misclassification of stratification factor will be analyzed as the actual (or ITT) analysis. A sensitivity analysis using the planned (or appropriate strata) will be performed. Seri+BB will be compared relative to pla+BB using a one-sided significance level at 0.025.

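### The SAP describes a different design (phase 3, 2:1, one-sided 0.025, 195 events, other strata), so it cannot deliver the protocol's 58-event, one-sided 0.10 primary analysis

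*SAP*

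**What the plan says.** **Protocol.** The synopsis gives the number MM-121-02-02-10 and a phase 2, double-blind comparison of seribantumab or placebo, each with fulvestrant, in 80 randomised patients. Section 10.2 fixes the test: "Statistical significance will be determined by using a one-sided type I error of 0.10". It also fixes the information: "A total of 58 PFS events will be required across two treatment arms randomized in a 1:1 ratio", for 80% power at HR 0.57 (medians 4 and 7 months). The synopsis starts the primary analysis at 58 events. Section 5.1 states: "Randomization will be stratified based on bone-only disease (yes, no) and geographic status (US, non-US". Section 10.5.1 asks for 80% confidence intervals, and section 10.3 makes the Per Protocol set the primary efficacy population.

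**SAP.** The introduction says the plan is for protocol seribantumab-02-03-10. Section 1.2 describes a "phase 3 trial of exemestane or fulvestrant with or without seribantumab". Section 5.1 states "Approximately 195 PFS events are be required to have at least 95% power to detect a 43% risk reduction", with 2:1 allocation, 286 patients and a futility interim at about half the events. On the cut-off, section 5.3.1 says: "A database snapshot will be determined at the time of the confirmed number of PFS events: 195 final", and it allows no snapshot before the minimum number of events. On the test, section 5.5.1 says: "Seri+BB will be compared relative to pla+BB using a one-sided significance level at 0.025". The strata listed there are "prior chemotherapy use (yes, no), chemotherapy backbone (exemestane or fulvestrant), and geographic region (US, Non-US/Non-Asia, Asia". Confidence intervals are 95%, and section 2.1 takes HRG-positive ITT patients as the primary efficacy population.

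SAP section 1.1, which is headed as covering protocol changes and clarifications, explains none of these differences.

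**The concern.** The protocol leaves detailed methodology, including PFS censoring, to the SAP, so the SAP is the document an analyst would follow. Followed literally, it waits for an event count the trial cannot produce, applies a stricter significance level than the one the trial was sized for, and stratifies on factors that were not used to randomise. Followed in part, it leaves two significance levels, two sets of strata and two primary populations on file. A choice between them could then be made after the data are seen, and that choice could decide whether the trial is called positive.

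**Working it through.** **1. The two designs side by side**

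| Item | Protocol | SAP |
|---|---|---|
| Protocol number | MM-121-02-02-10 (synopsis) | seribantumab-02-03-10 (1) |
| Phase and backbone | 2, fulvestrant (synopsis) | 3, exemestane or fulvestrant (1.2) |
| Allocation | 1:1 (10.2) | 2:1 (5.1) |
| Patients | 80 (10.2) | 286 (5.1) |
| PFS events | 58 (10.2) | 195 (5.1, 5.3.1) |
| One-sided alpha | 0.10 (10.2) | 0.025 (5.1, 5.5.1) |
| CI for PFS | 80% (10.5.1) | 95% (5.3.2) |
| Strata | bone-only; US/non-US (5.1) | prior chemotherapy; backbone; three-level region (3.7, 5.5.1) |
| Interim | none specified | futility, about 50% of events (5.1) |
| Primary population | Per Protocol (10.3) | HRG-positive ITT (2.1) |

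**2. Each document's own figure**

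Schoenfeld's formula, with p the proportion allocated to one arm:

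events = (z_alpha + z_power)² / [p(1−p)(ln HR)²], with ln 0.57 = −0.562 and (ln 0.57)² = 0.316.

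- Protocol: (1.282 + 0.842)² / (0.25 × 0.316) = 57.1, or 57.6 with HR taken as 4/7. Both round up to 58, so the protocol's figure reproduces.
- SAP: power = Φ(√(195 × 2/9) × 0.562 − 1.960) = Φ(3.70 − 1.96) = 95.9%. The claim of at least 95% also reproduces.

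These are two coherent designs, so 195 is not a slip of arithmetic.

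**3. Can the SAP's cut-off be reached?**

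Each patient contributes at most one first PFS event, so 80 patients give at most 80. Both 195 and the interim at 0.5 × 195 = 97.5 events are out of reach. Assuming exponential PFS, uniform accrual and no dropout, the protocol's 16-month accrual and 20-month duration yield about 60 events, which agrees with 58.

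**4. The SAP's alpha at the protocol's 58 events**

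Power = Φ(√58/2 × 0.562 − z_alpha) = Φ(2.140 − z_alpha).

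- One-sided 0.10: Φ(2.140 − 1.282) = 80.5%.
- One-sided 0.025: Φ(2.140 − 1.960) = 57.2% (56.8% at HR 4/7).

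The largest observed HR that is significant is exp(−2 z_alpha/√58):

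- One-sided 0.10: 0.714.
- One-sided 0.025: 0.598.

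An observed HR between about 0.60 and 0.71 therefore gives opposite conclusions. If the true HR is 0.57, that happens in about 80.5 − 57.2 = 23.3% of trials. Restoring 80% power at 0.025 with 1:1 allocation needs (1.960 + 0.842)² / (0.25 × 0.316), which rounds up to 100 events (101 at HR 4/7), more than the 80 patients.

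**5. Strata**

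- SAP 3.7 defines the chemotherapy factor as treatment for locally advanced or metastatic disease. Protocol exclusion criterion 4.2 b rules that out, so the factor is constant for eligible patients.
- Backbone is constant, because every patient receives fulvestrant.
- The Asia level should be empty, because the synopsis places the trial in North America and Europe.
- Bone-only disease, a randomisation factor, does not appear.

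The SAP's test therefore reduces to stratification by US/non-US alone.

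**The case against.** Several points on the other side are fair.

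- **The protocol arguably governs.** Protocol section 10 lets the SAP modify plans but says a major change to the primary analysis will also appear in a protocol amendment. The protocol supplied keeps 58 events and 0.10, which favours those figures. It does not make the SAP usable, since the protocol leaves the detail to it.
- **The 57.2% describes a hybrid.** The SAP pairs 0.025 with 195 events and forbids an earlier snapshot, so read strictly it gives no verdict at 58 events. This stands: the power loss is conditional on applying the SAP's alpha at the protocol's event count. The strict reading is no better, because the analysis then never happens.
- **Constant strata do no harm.** True: they drop out of a stratified log-rank test. Also, SAP 5.5.1 lists prior chemotherapy without naming a setting, and adjuvant chemotherapy is allowed, so on that wording alone the factor could vary. SAP 3.7 settles the meaning. The real loss is bone-only disease, and its size cannot be computed from the documents.
- **Protocol 10.1 is not a second alpha.** Its one-sided 0.025 is a default that yields where another level is stated, and 10.2 states 0.10. This stands. The sentence allowing only 95% intervals has no such qualifier and does conflict with the 80% intervals in 10.5.1.
- **The DMC charter may cover an interim.** The protocol gives the DMC a role in evaluating efficacy under a charter that was not supplied. The protocol itself still specifies no interim analysis.
- **A matching SAP may exist.** The documents cannot exclude this, nor show whether the present SAP belongs to another trial or to a phase 3 plan that was not updated. The defect in the supplied SAP is the same either way.

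**Conclusion.** The concern holds, and it must be fixed before the primary analysis. The SAP's data cut-off is impossible in an 80-patient trial. That needs no modelling assumption. Its significance level, confidence level, allocation, strata and primary population all differ from the protocol's. Using its alpha at 58 events would lower power from 80.5% to 57.2% and move the success boundary from an observed HR of 0.714 to 0.598. Those figures assume proportional hazards, a true HR of 0.57, 1:1 allocation and Schoenfeld's approximation without adjustment for stratification. HR 4/7 in place of 0.57 changes the power by less than half a percentage point.

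**What to change.** Issue a SAP for this protocol before database lock and unblinding. If a matching one already exists, supply it. It should contain:

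- the correct protocol number, phase 2, 1:1 allocation, and treatment columns for seribantumab + fulvestrant and placebo + fulvestrant only;
- the primary data cut-off at 58 PFS events;
- a stratified log-rank test at one-sided 0.10, with 80% confidence intervals for the hazard ratio and medians;
- strata of bone-only disease (yes/no) and region (US/non-US);
- the protocol's Per Protocol primary population, with the ITT analysis alongside;
- PFS censoring reconciled with follow-up: protocol 3.1 and 7.7 continue scans after treatment stops until progression, while SAP 3.1 generally censors at discontinuation and counts later events only within 30 days.

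Remove the 195-event cut-off, the 2:1 sample size, and the backbone and prior-chemotherapy strata. Delete the futility interim, or add it to the protocol if it is wanted. In protocol 10.1, limit the 0.025 level and the 95% intervals to analyses other than primary PFS. If the sponsor prefers any of the SAP's choices for the primary analysis, protocol section 10 requires an amendment.

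The cost is a SAP rewrite and a short protocol amendment, which under protocol 11.8 goes to the IRB/EC unless purely administrative. No added patients, data or procedures are needed.

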## 5.1.1 Safety Review and Interim Analysis

An independent external DMC will monitor the safety of the patients on a periodic basis. The DMC will provide a recommendation to Merrimack based on periodic safety review and/or the interim analysis whether to terminate the trial early due to safety or futility. Additionally the DMC will make a data recommendation about early termination due to observed results. In an attempt to minimize bias the interim analysis will be generated by an unblinded external vendor who will communicate results directly to the DMC. The DMC will discuss the efficacy recommendation with the Merrimack Steering Committee, if necessary. Details of the interim analysis and Steering Committee will be described in the DMC Charter.

## 5.2 General Considerations

All analyses discussed in this SAP will be generated for the final CSR. All datasets, documentation, and the SAP will be archived in the Trial Master File (TMF). Tables, figures, and listings (TFLs), as described in this document and in the mock shells, will be created using SAS version 9.2 or higher. Mock table, listing, and figure shells will be developed for detailed information on the layout. The mock tables, listings, and figure shells will not be considered as part of the SAP signoff.

## 5.3 Standards

The information presented in this section describes the standard displays/mocks and analysis to be performed. Standard table displays will include columns for treatment groups called: seribantumab+fulvestrant/exemestane (seri+BB), seribantumab+fulvestrant (seri+f), seribantumab+exemestane (seri+e), placebo+fulvestrant/exemestane (pla+BB), placebo+fulvestrant (pla+f), placebo+exemestane (pla+e), and Overall. The primary comparisons are based on seri+BB versus pla+BB.

Continuous variables, as deemed appropriate, will be summarized using the number of non-missing observations, mean, standard deviation, median, minimum and maximum values. Missing data values will be treated as missing in summarization. No imputation of missing data will be performed.

Categorical variables will be summarized using the number of non-missing observations, frequency and percentage out of the number of non-missing observations in each category. Percentages will be presented to one decimal place (e.g., xx.x). Percentages will not be presented when zero counts occur.

Enrolled will be defined as those patients signing informed consent and completing entry criteria.

All p-values will be presented as two-sided using a SAS format (pvalue5.3). Primary efficacy inferential analyses will be tested against a one-sided, alpha at 0.025 (i.e., two-sided 0.05) unless stated otherwise.

## 5.3.1 Data Cut-off

A database snapshot will be determined at the time of the confirmed number of PFS events: 195 final. The snapshot will not be performed until the minimum number of PFS events have occurred. The snapshot will include all data entered and cleaned up to that particular point in the study and data will not be changed, edited, or updated on or prior to this particular date. A separate snapshot of this data will be maintained in the biostatistics and programming area. Patients that have completed the study will require investigator signature. Continuing patients will have data reviewed and approved. Data entered after the data cut-off dates will continue to be cleaned but not reported at the time of the interim or final analysis.

A final database lock will be performed upon determination of the final PFS event. Any necessary changes to previously entered data will be documented. The final database lock will include all data for all timepoints and will be conducted at a later timeframe. Site investigators will provide signatures for any remaining patient data which was outstanding at the time of soft lock.

## 5.3.2 Analysis of Key Time-to-Event Endpoints

Time-to-event endpoints between two treatment arms will be compared with a 1-sided,  $\alpha = 0.025$ , stratified logrank test, unless specified otherwise. Stratification factors will include: prior chemotherapy use (yes, no), chemotherapy backbone (exemestane or fulvestrant), and geographic region (US, Non-US/Non-Asia, Asia). Stratified Cox proportional hazards models will be constructed with stratification factors and treatment in the model to estimate hazard ratio and 2-sided 95% confidence interval (CI).

Additional comparisons between treatment groups will be performed using an unstratified log-rank test. Cox proportional hazards model with treatment group only will be constructed to estimate the hazard ratio and 2-sided 95% confidence intervals.

Potential influences of other baseline patient characteristics on various populations may be explored. Candidate covariates for the multivariate model will be selected using a stepwise selection process with treatment always in the model. Only covariates significant at a 15% level will be entered in the model and covariates significant at

15% will be considered for the final multivariate model. Treatment-by-covariate effects will be explored only for the set of factors included in the final model. The estimated hazard ratio and 2-sided 95% CI will be reported. Forest plots will be displayed for subgroup analyses.

The assumption of proportional hazards will be explored using a variety of graphical displays and testing. Hazard ratios and log (-log) of the survival probability estimates over time will be graphed. A scatterplot of smoothed Schoenfeld residuals over log of time will be displayed to check the primary efficacy analysis assumptions. The assumption of proportional hazards will be reviewed for the primary efficacy endpoint using the available graphical information. No formal testing will be performed in place of the stratified log-rank, if the assumption of proportional hazards does not hold.

Kaplan-Meier methods will be used in estimating the probability of event and displayed graphically. Time-toevent calculations will be performed in months unless specified otherwise. Median event times and 2-sided 95% CI will be provided based on Brookmeyer-Crowley methods. Probability of event estimates at 6, 9, 12, 15, and 18 month intervals will be reported in tables.

## 5.3.3 Analysis of Key Binary Endpoints

Frequencies and percentages will be reported for binary endpoints. The rate of binary endpoints between 2 treatment arms will be compared using a Cochran Mantel-Haenszel (CMH) test stratified according to the stratification factors and a Pearson  $\chi^2$  test, both at a 2-sided,  $\alpha = 0.05$  level. The relative risk ratio estimate will be used to contrast treatment effects on response rates. Point estimates of the rates for each treatment arm will be provided along with the corresponding exact 2-sided 95% CI using exact methods based on the binomial distribution.

## 5.3.4 Analysis of Continuous Endpoints

Mean, standard deviation, median, minimum, maximum will be reported for continuous endpoints. Least-squares mean and standard error with 95% confidence intervals will be reported for models. Models will be tested using a 2-sided,  $\alpha = 0.05$  level.

## 5.4 Baseline Analysis

## 5.4.1 Disposition, Populations, and Patients Excluded from Population

Treatment termination and study termination will be summarized overall and by reason. Included in the summarization will be deaths. Overall number of deaths, deaths on-treatment (up to 30 days post last dose date), deaths after treatment.

A listing of patients and those excluded from a population along with reason will be provided, if available.

Protocol deviations will be listed and major protocol deviations will be summarized.

## 5.4.2 Demographics, Cancer Diagnosis, Medical History

Descriptive statistics will be reported for Age (years), sex (male, female), race (white/Caucasian, Black or African American, Alaska native or American Indian, Asian/Oriental, Native Hawaiian or Pacific Islander, other), height (cm), weight (kg), ethnicity, and ECOG at baseline. Other cancer diagnosis factors such as frequency of adenocarcinoma, squamous cell; TNM Stage; Bone disease, brain metastisis, visceral metastisis, number of prior chemotherapies, EGFR mutation status, KRAS status, best response will be reported. Time from cytological or histo-pathologic diagnosis to randomization will be analyzed as a continuous parameter.

Stratification factors will be summarized by frequencies and percentages. Frequency of patients randomized within each site by country will be summarized.

Prior surgical therapy (yes/no), prior radiation therapy (yes/no) will be characterized.

Medical history will be coded using the latest version of MedDRA coding. Medical history will be summarized by System Organ Class and preferred term.

